### **Exclusion Criteria**

Subjects will be excluded from the study if they meet any of the following criteria:

1. Subjects with evidence of untreated primary sleep disorders (e.g., Obstructive Sleep Apnea, Restless Legs Syndrome, Periodic Leg Movements of Sleep) as determined in the sleep screening questionnaire and clinical history.
2. Subjects who have a DSM-IV diagnosis of substance dependence or abuse (with the exception of nicotine) that has been active within the past 6 months.
3. Subjects taking exclusionary medications, such as benzodiazepines/benzodiazepine receptor agonists, tricyclic antidepressant medications or antipsychotics as these medications have been reported to cause SRED, who are unable or unwilling to complete the required washout of these medications.
4. Subjects with an active or unstable major psychiatric disorder requiring further treatment (e.g., major depressive disorder). Subjects with clinically significant depression defined by a HAM-D >20 or who, in the investigator's judgment might require intervention with either pharmacological or non-pharmacological therapy over the course of the study, will also be excluded.
5. Subjects with an active daytime DSM-IV-TR™ diagnosis of Anorexia Nervosa or Bulimia Nervosa within the 3 months prior to screening.
6. Subjects judged clinically to be at serious suicidal or homicidal risk.
7. Subjects with a body mass index (BMI)  $\geq 50$  kg/m^2.
8. Subjects who have positive urine drug screening (phencyclidine, cocaine, amphetamines, tetrahydrocannabinol, and opiates) at Visit 1 (Day -14).
9. Subjects who report consumption of more than 2 alcoholic beverages daily, 14 or more alcoholic beverages weekly
10. Subjects who report consumption of more than 4 beverages containing caffeine daily.

11. Subjects who are rotating or third shift workers.
12. Subjects who are pregnant or lactating.
13. Subjects with a history of recurrent nephrolithiasis or on another carbonic anhydrase inhibitor.
14. Subjects with progressive or degenerative neurological disorders or a structural disorder of the brain from birth, trauma or past infection.
15. Subjects who have recently had or are planning to have surgery.
16. Subjects who have previously been treated with topiramate and discontinued treatment due to an adverse event or subjects with a known hypersensitivity to topiramate.
17. Subjects who have previously taken Topiramate.
  
18. Subjects known to have clinically significant, unstable medical conditions as determined by careful clinical interview and review of medical records, including but not limited to:
  - Symptomatic coronary artery disease or peripheral vascular disease
  - Malignancy or history of malignancy within the past 5 years (except basal cell carcinoma)
  - Clinically significant renal disease including creatinine >1.5 or creatinine clearance (calculated by standard method) <60
  - Clinically significant diseases of the gastrointestinal system including active liver disease with a history of LFTs >3x ULN as determined by review of medical history or records
  - Any disease or condition that compromises the function of those body systems that could result in altered absorption, excess accumulation, or impaired metabolism or excretion of topiramate
19. Subjects who have participated in an investigational drug or device trial within the 4 weeks prior to enrollment.
20. Subjects who in the opinion of the investigator should not be enrolled in the study because of the Precautions, Warnings or Contraindications sections of the topiramate package insert.
21. Subjects with glaucoma.

## **STUDY MEDICATION AND SUPPLIES**

### **Study Treatments**

The study medication will consist of 25 mg or 100 mg of topiramate tablets, or matching placebo, prepared in identically appearing capsules by the MGH IDS. The medication will be titrated over a 9-week period according to the following suggested schedule:

### **Titration Schedule \***

Double-Blind Topiramate / Placebo Dosing				
Days	Study Medication		Total Daily Dose	
	25 mg Tablets	100 mg Tablets	Topiramate	Placebo
1-7	1 capsule		25 mg	Matching capsules
8-14	2 capsules		50 mg	
15-21	3 capsules		75 mg	
22-28	4 capsules		100 mg	
29-35	5 capsules		125 mg	
36-42	6 capsules		150mg	
43-49		2 capsules	200mg	
50-56	2 capsules	2 capsules	250 mg	
57+		3 capsules	300 mg	

Subjects will be instructed to take the study medication one hour prior to bedtime (h.s.). Subjects will be informed during the consent process that they may be asked to take up to six pills at different points during the titration period. The study medication will be titrated to 300 mg/day or the subject's minimum effective dose (MED).

At the investigator's discretion the titration rate may be adjusted. However, after the second week of titration, subjects must take at least 25 mg/day of topiramate or matching placebo for the duration of the double-blind phase. During the maintenance period, subjects should remain at the dose attained at the end of the titration period, however dose adjustments will be permitted at the discretion of the investigators.

Subjects will taper their study medication by decreasing the dose by approximately 30% every three days over approximately a 14-day period until they are no longer taking study medication.

\*Subjects with an estimated creatinine clearance <70 but >60 will be included in the study, but will follow a modified titration schedule. Dose increases for these subjects will be take place no less than every 14 days rather than every 7 days, and at the end of the titration period they will reach a maximum dose of 125mg. During the maintenance period, subjects should remain at the dose attained at the end of the titration period, however dose adjustments will be permitted at the discretion of the investigators up to a maximum dose of 150mg.

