### **Inclusion Criteria**

Subjects must satisfy the following criteria before entering the study:

1. Subjects must have a diagnosis of the following for at least 6 months:  
  
Sleep-Related Eating Disorder, defined as (according to ISCD-2 criteria):
  - A. Recurrent episodes of involuntary eating and drinking occur during the main sleep period.
  - B. One or more of the following must be present with the recurrent episodes of involuntary eating and drinking:
    - i. Consumption of peculiar forms or combinations of food or inedible or toxic substances
    - ii. Insomnia related to sleep disruption from repeated episodes of eating, with a complaint of nonrestorative sleep, daytime fatigue, or somnolence
    - iii. Sleep related injury
    - iv. Dangerous behaviors performed while in pursuit of food or while cooking food
    - v. Morning anorexia
    - vi. Adverse health consequences from recurrent binge eating of high-caloric foods
  - C. The disturbance is not better explained by another sleep disorder, medical or neurologic disorder, mental disorder, medication use, or substance use disorder
2. Subjects must experience 3 nights per week of nocturnal eating during the 14-day prospective baseline period prior to Visit 2.
3. Subjects must be between 18 and 75 years of age.
4. Subjects must be able to take oral medication in capsule form, adhere to medication regimens and be willing to return for regular visits.
5. Subjects must have observed the designated washout periods for prohibited medications outlined under the Concomitant Therapy section of this protocol.
6. Female subjects must be:
  - postmenopausal for at least one year, surgically sterile, or
  - practicing an effective method of birth control (e.g., contraceptive injections, intrauterine device, double-barrier method, contraceptive patch, male partner sterilization, abstinence)

and agree to continue abstinence or to use an acceptable method of contraception, as listed above, should sexual activity commence) before entry and throughout the study

- If taking prescription oral contraceptives, must agree to also use a barrier method of birth control throughout the study since topiramate may affect the metabolism of prescription oral contraceptives.
  - Have a negative urine pregnancy test at Visit 2 (Day 1).
7. Subjects must be able to read and comprehend written instructions, and be willing and able to comply with protocol requirements.

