#### Visit 1\* (Day -14)

1. Review inclusion/exclusion criteria
2. Assess concomitant medications
3. Obtain weight
4. Obtain non-fasting clinical laboratory tests as follows:
  - Urine Drug Screen [cocaine, amphetamines, methamphetamines, benzodiazepines, tetrahydrocannabinol (THC), and opiates].
  - Hemoglobin A1C
  - Creatinine (creatinine clearance will be calculated using standard formula)
5. Perform urine pregnancy test (subjects of childbearing potential only)
6. Administer the Three Factor Eating Questionnaire (TFEQ)
7. Administer the Sheehan Disability Scale
8. Dispense sleep and night eating diary
9. Record adverse events
10. Schedule return visit

\*Visits 1A and 1 may be combined for subjects who do not require washout from prohibited medications.

Subjects who are eligible for study entry based on the results of the above will be instructed to return for Visit 2 (Day 1).

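### A creatinine clearance of exactly 60 meets neither the renal exclusion nor the modified-titration rule, so it falls by default to the standard dosing table

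*Combined protocol and SAP*

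**What the plan says.** Three places in the combined protocol and SAP use creatinine clearance.

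- **Exclusion Criteria, item 18**, lists among its excluded conditions "Clinically significant renal disease including creatinine >1.5 or creatinine clearance (calculated by standard method) <60".
- **Titration Schedule, footnote**: "Subjects with an estimated creatinine clearance <70 but >60 will be included in the study, but will follow a modified titration schedule". For these subjects, "at the end of the titration period they will reach a maximum dose of 125mg", and maintenance adjustments are allowed "up to a maximum dose of 150mg".
- **Visit 1 (Day -14)**: "Creatinine (creatinine clearance will be calculated using standard formula". No equation, body weight, unit or rounding rule is given here or elsewhere.

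Everyone else follows the main table: "The study medication will be titrated to 300 mg/day", or to the subject's minimum effective dose if that is lower. Study Treatments describes the table as a suggested schedule. Pharmacokinetic Profile names the kidney as the main route of elimination, with about 70% of a dose recovered unchanged in urine.

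**The concern.** The exclusion stops just below 60 and the modified band starts just above it. The value 60 belongs to neither, so only the general table is left for it. A subject there would have a higher dose target than one with slightly better renal function, for a drug that the protocol describes as mainly cleared by the kidney.

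The classification is also made only once. The visit lists and the Time and Events Schedule show creatinine at Visit 1 and nowhere later, so no scheduled measurement would bring a subject at the boundary back for reclassification.

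The missing definition of the calculation makes the boundary less sharp. Without a rounding rule it is unclear which results count as 60. Without a stated equation and body weight, the number compared with 60 and 70 is not fixed.

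**Working it through.** **1. The footnote's own figure.** One 25 mg step every 14 days, starting at 25 mg, gives 25 mg (days 1-14), 50 mg (15-28), 75 mg (29-42), 100 mg (43-56) and 125 mg from day 57. That lies within the 9-week (63-day) titration, so the 125 mg ceiling agrees with the schedule. The problem is only in who is assigned to it.

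**2. The two rules side by side** (creatinine not above 1.5):

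| Clearance | Exclusion 18 (<60) | Footnote (>60 and <70) | Result as written |
|---|---|---|---|
| 59.9 | met | not met | excluded |
| 60 | not met | not met | standard table, target up to 300 mg/day |
| 60.1 to 69.9 | not met | met | capped at 125 mg, then 150 mg |
| 70 and above | not met | not met | standard table, target up to 300 mg/day |

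The ceilings on either side of 60.1 differ by 300/125 = 2.4 at the end of titration and 300/150 = 2.0 in maintenance. A step of the same size exists by design at 70. Only the direction of the step at 60 is anomalous.

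**3. How many subjects.** The documents give no distribution of clearance, so this part rests on assumptions. Suppose results are rounded to whole numbers, so that about 59.5 to 60.5 is recorded as 60, and that clearance is normal with mean m and SD s. Then P(60) = Φ((60.5 − m)/s) − Φ((59.5 − m)/s), and the expected number is 40 × P(60).

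| m, s (assumed) | P(60) | Expected of 40 |
|---|---|---|
| 90, 20 | 0.0065 | 0.26 |
| 110, 30 | 0.0033 | 0.13 |
| 120, 30 | 0.0018 | 0.07 |

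With 1:1 allocation, half of these would receive active drug: about 0.04 to 0.13 subjects. Without rounding, a result of exactly 60 is rarer still.

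**4. Secondary check: the unstated calculation.** Assumed equation, not in the documents: Cockcroft-Gault, (140 − age) × weight / (72 × creatinine in mg/dL), × 0.85 for women. Adjusted weight is taken as ideal + 0.4 × (actual − ideal).

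Take a woman of 60, 160 cm, BMI 45, creatinine 1.1 (assumed). Actual weight is 1.60² × 45 = 115.2 kg. Ideal weight is taken as 52.4 kg. Adjusted weight is 52.4 + 0.4 × 62.8 = 77.5 kg. The multiplier is 80 × 0.85 / (72 × 1.1) = 0.859 per kg.

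- Actual weight: 98.9, standard table.
- Adjusted weight: 66.5, modified schedule.
- Ideal weight: 45.0, excluded.

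The split does not need extreme obesity. A woman of 60, 165 cm, BMI 30, creatinine 1.0 gives 77.1 / 63.1 / 53.7 in the same order. It is not general either: a man of 50, 178 cm, BMI 38 stays on the standard table under all three weights for creatinine 0.8 to 1.3. On an even grid (age 18-75, BMI 30-49, creatinine 0.6-1.5, both sexes), 43.5% of cells change class with the weight used and 10.1% span all three classes. These are shares of grid cells, not of expected patients.

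Rounding interacts with the gap. For a woman of 60, 165 cm, BMI 30, creatinine 0.9, ideal weight gives 59.7. She is excluded if the value is kept as it is, and under neither rule if it is rounded to 60.

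**The case against.** The strongest reply is that the gap is a missing equals sign that would rarely matter in practice. One boundary value is involved, and well under one subject is expected there. The 300 mg figure is a target in a suggested schedule that can stop at the minimum effective dose, and the investigator may slow titration or adjust the maintenance dose. Other provisions also apply. Item 18 separately removes conditions that could impair excretion of the drug, and item 20 lets the investigator exclude on the basis of the package insert. All of this stands, and it keeps the point small. It does not close the gap, because none of these provisions says which class a value of 60 belongs to.

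A reader might infer that these limits are the trial's only renal protection. The provisions just listed, and the separate serum creatinine limit, show otherwise.

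A reader might also infer that the unnamed formula will send equal subjects to different classes depending on who calculates. The documents do not support that. This is a single-center pilot that may well apply one convention throughout, and the three-way split rests on an equation and weight conventions found nowhere in the protocol. What remains is missing detail that is worth writing down.

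**Conclusion.** The point holds as a minor defect. That exactly 60 is unassigned follows from the text alone and needs no assumption. Its expected reach, about 0.07 to 0.26 of 40 subjects, rests on assumed normal distributions and whole-number rounding. The dependence on body weight is shown only under an assumed Cockcroft-Gault equation and only for some obese profiles, so it is a secondary wording point.

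The footnote should not be read as meaning to give subjects at 60 the full 300 mg. That result arises by omission, and 300 mg is a ceiling rather than the dose such a subject would necessarily reach.

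The efficacy comparison is not threatened. The class is set from a creatinine taken at Visit 1, before randomization at Visit 2, and the same rule applies in both arms. The point concerns an unambiguous operating rule and the safety of an occasional subject at the boundary.

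**What to change.** Reconcile exclusion 18 with the Titration Schedule footnote so that every clearance value, including 60, falls under exactly one rule. Which rule takes 60 is a clinical decision for the sponsor.

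In the same edit, state one calculation: the equation, the body weight and the visit it comes from (weight is taken at both Visit 1A and Visit 1), the units, and whether the result is rounded before it is compared with the limits. Refer to that calculation from exclusion 18, the footnote and the Visit 1 procedures. The choice of equation and weight is also the sponsor's.

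The cost is wording in three places. Creatinine, height and weight are already collected, and no visit, sample or analysis changes. The one side effect is that fixing the calculation may reclassify a few obese subjects compared with whatever convention the site now uses.

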### **Study Medication Packaging**

Medication will be prepared and packaged by the MGH IDS Pharmacy. For the first 6 weeks of the titration period the investigator will dispense bottles with sufficient 25mg capsules for 7+3 days of the necessary dose. After the subject reaches a dose of 150 mg the medications will be packaged in bottles as prescribed by the investigator depending on the dose and number of tablets needed. All study medication will be dispensed in child-resistant packaging. Bottles will be labeled with the patient name and ID and the dosing information. Bottles will be clearly labeled as containing either 25 mg or 100 mg matching placebo or topiramate tablets.

Subjects will be dispensed the appropriate number of tablets needed until they return for their next office visit. Study medication should be stored at room temperature 15-30°C (59-86°F), be protected from moisture, and be maintained in a secure area.

### **Study Medication Accountability and Compliance**

Starting at Visit 2 (Day 1), study medication will be dispensed to each subject with instructions to return all unused medication and packaging (including empty bottles) at the next study visit in order to assess compliance. Returned study medication bottles may be redispensed to the same subject if appropriate. Additional bottles will be dispensed to each subject as needed.

All study medication dispensed by the investigator or designee will be accounted for throughout the study. Information about subject dosing and compliance will be recorded in the subject's study records.

Subjects who are noncompliant with medications (according to pill counts and diaries) may be removed from the study at the discretion of the investigators.

The investigator agrees not to allow access to the study medication to any person except those named as sub-investigator(s) or clinical care staff, and dispense only to qualified subjects participating in the study.

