### **Blinding**

The randomization code will be maintained by the MGH IDS Pharmacy and will not be revealed to study subjects, investigators or clinical staff until all subjects have completed and the database has been finalized.

To maintain the blind, sealed envelopes containing the study drug identification (e.g., active or placebo) will be provided to the investigator. These sealed envelopes will be kept together, in a limited access area that is accessible 24 hours per day. The study drugs will be identical in appearance and will be packaged in identical containers.

Under normal circumstances, the blind should not be broken. The blind should be broken only if specific treatment would be dictated by knowing the treatment status of the subject. Individual code breaks by the investigator will normally result in withdrawal of the subject from the trial. The date, time and reason for the unblinding must be documented in the study files.

***After the termination of the double-blind portion of the study, subjects can be made aware of the study medication they were given at their request.***

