#### Visit 8 (Day 91)

1. Assess concomitant medications
2. Perform physical examination
3. Obtain weight
4. Administer the Medical Outcome Study (MOS) Sleep Scale
5. Administer the Epworth Sleepiness Scale
6. Administer the HAM-D
7. Administer the TFEQ

8. Administer the SDS
9. Obtain blood sample for HbA1C
10. Collect and review sleep and night eating diary
11. Collect study medication and perform drug accountability
12. Record adverse events
13. Dispense medication and instruct the subject on tapering.
14. Schedule Post-Taper Visit 9 (Day 105) in approximately 2 weeks

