### **Early Withdrawal**

Subject participation may be terminated based upon subject choice, protocol violation (e.g., non-compliance), adverse event, or if a subject is lost to follow-up. The primary reason for withdrawal should be clearly indicated in the subject's study file.

In the event that a subject discontinues prematurely, final visit procedures will be performed at the time of discontinuation, if possible. Subjects who discontinue prematurely should be scheduled promptly for final visit (Visit 8, Day 91) procedures, preferably within 24 hours of the last dose. Subjects should taper study medication as discussed under Study Treatments. All adverse events should be followed to resolution, if possible. All unused study medication must be returned to the investigator.

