### **Efficacy Analyses**

The efficacy analyses will be performed on an intent-to-treat (ITT) population defined as all randomized subjects who were dispensed study medication and for whom one post-baseline efficacy measurement is available.

Efficacy analyses will be conducted separately for subjects with night eating syndrome or sleep-related eating disorder, and across all subjects with either of these two diagnoses. The primary efficacy parameter will be the change in the number of nights per week of the specified nocturnal eating episode.

The primary efficacy parameter of number of nights per week with nocturnal episodes will be analyzed using ANCOVA with baseline frequency of nocturnal episodes as a co-variate. Diagnostic procedures will be conducted to determine whether the statistical assumptions are met.

The MOS, SDS, TFEQ, HAM-D, HbA1C, body weight and Epworth Sleepiness Scale will be analyzed using an ANCOVA with the baseline value as a covariate.

Information obtained from the sleep diaries will be summarized.

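### Subjects removed from the study for medication noncompliance, an adverse event or a code break have no eating-night data planned after removal, which leaves the ITT comparison open to bias of unknown size

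*Combined protocol and SAP*

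**What the plan says.** Three sections let a randomized subject's participation end, and not only the study drug. Study Medication Accountability and Compliance: "Subjects who are noncompliant with medications (according to pill counts and diaries) may be removed from the study at the discretion of the investigators". Early Withdrawal: "Subject participation may be terminated based upon subject choice, protocol violation (e.g., non-compliance), adverse event, or if a subject is lost to follow-up". Blinding: "Individual code breaks by the investigator will normally result in withdrawal of the subject from the trial". Only the first of these gives the investigator discretion in terms, and it sets no threshold.

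For what follows, Early Withdrawal states: "In the event that a subject discontinues prematurely, final visit procedures will be performed at the time of discontinuation, if possible". It adds: "Subjects who discontinue prematurely should be scheduled promptly for final visit (Visit 8, Day 91) procedures, preferably within 24 hours of the last dose". The Visit 8 list includes "Collect and review sleep and night eating diary", but neither that list nor the Time and Events Schedule has a new diary dispensed at Visit 8. After that visit the section describes only tapering, return of unused medication and safety follow-up: "All adverse events should be followed to resolution, if possible". No section describes a subject who stays in the study off drug.

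Under Efficacy Analyses, "The efficacy analyses will be performed on an intent-to-treat (ITT) population". That population is randomized subjects who received study medication and have a post-baseline efficacy measurement. The primary variable is the change in nights per week with nocturnal eating, analysed by ANCOVA with baseline as covariate. No endpoint week, averaging window or missing-data rule is given.

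**The concern.** An intent-to-treat comparison needs outcomes on randomized subjects whether or not they kept taking their capsules. Here the conduct rules tie leaving the study to events that can follow from treatment: missed capsules, adverse events and code breaks. Nights that were never recorded cannot be recovered by any later analysis.

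What is at stake is the maintenance-period comparison. If the subjects who leave would have done worse than those who stay, and more of them leave one arm than the other, the observed difference partly reflects who stayed. With a goal of 40 randomized subjects, a few such losses count.

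**Working it through.** **1. Which nights are lost.** Overview of Study Design gives titration of up to 9 weeks (9 x 7 = 63 days) and maintenance of 4 weeks (28 days); 63 + 28 = 91, the day of Visit 8. A subject removed on Day d, with d no later than 63, can supply diary nights up to d and 0 of the 28 maintenance nights.

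**2. Whether removal could be related to outcome.** Randomization and Blinding keep the investigator blind to arm. But the daily diary described under Study Evaluations records both night eating and tablets taken, and it is reviewed at the visits where drug accountability is done (Visits 3 to 8). Whoever judges compliance can therefore see the subject's response. Medication Side Effects lists further dose-related events above 200 mg/day and titration goes up to 300 mg/day, so unequal compliance between arms is plausible. Lack of benefit on placebo would work in the other direction.

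**3. The only discontinuation figure used from the documents.** In the 17-patient case series under Preliminary Reports with Topiramate, 6 stopped (6/17 = 35%): 4 for lack of efficacy and 2 for side effects. All 11 who continued were controlled (11/11), against 11/17 = 65% of those treated. Stopping was tied to outcome there. However, these patients stopped medication; none is described as removed by an investigator for noncompliance. I use 35% only as a high-end scenario.

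**4. Arithmetic of loss.** The plan states no power, SD or dropout, so there is no figure to reproduce. If a fraction q of an arm is lost and those subjects are D nights/week worse than the rest, the retained arm mean is too low by q x D. For D from 1 to 3 (assumed):

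| q | error in arm mean, nights/week |
|---|---|
| 10% | 0.10 to 0.30 |
| 20% | 0.20 to 0.60 |
| 35% | 0.35 to 1.06 (from 6/17) |

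The error in the treatment difference is q1 x D1 - q0 x D0. It is zero when loss and D are equal in the two arms.

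**5. Simulation with no true effect.** Assumptions: 20 per arm, SD 2 nights/week, baseline correlation 0.5, 4,000 runs. Lost subjects are left out of the ANCOVA. Within an arm, those with the worst removal score are lost; rho is the correlation of that score with the baseline-adjusted outcome. Negative bias favours topiramate.

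| Loss, drug vs placebo | Bias at rho 0 / 0.3 / 0.6 | Type I error at rho 0 / 0.3 / 0.6 |
|---|---|---|
| 10% vs 10% | 0.00 / -0.02 / 0.00 | 0.056 / 0.045 / 0.062 |
| 20% vs 20% | 0.01 / -0.02 / -0.01 | 0.055 / 0.059 / 0.058 |
| 10% vs 0% | 0.00 / -0.11 / -0.18 | 0.054 / 0.059 / 0.065 |
| 20% vs 5% | 0.01 / -0.10 / -0.24 | 0.043 / 0.059 / 0.074 |
| 35% vs 10% | -0.01 / -0.17 / -0.37 | 0.045 / 0.059 / 0.108 |

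Bias appears only when loss is both outcome-related and unequal. The simulation error of a type I rate near 0.05 is sqrt(0.05 x 0.95/4000) = 0.003. The values of 0.059 are within the range seen under equal loss (0.045 to 0.062); 0.074 and 0.108 are clearly outside it.

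**6. Scale.** With 20 per arm and SD 2, the difference detectable with 80% power at two-sided 0.05, without baseline adjustment, is 2 x sqrt(2/20) x (1.960 + 0.842) = 1.77 nights/week. A bias of 0.17 to 0.37 is about 10% to 21% of that.

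**The case against.** The case on the other side is substantial. Removal is decided blind. The diary is collected at each clinic visit and again at the early final visit, and a removed subject with one post-baseline measurement stays in the analysis. Tolerability on topiramate and lack of benefit on placebo could both cause loss, so the net direction is unknown. The trial is a pilot whose sample size has no statistical basis. It can also be said that the real gap is the missing endpoint window and missing-data rule.

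Most of this limits the size of the point. It does not remove it. Blinding hides the arm but not the response. Data up to removal are not maintenance-period data. A missing-data rule is needed as well, but it would have to replace with assumptions what a diary could have recorded.

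A reader might go further than the documents allow in four ways:

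- That poor diary-keeping is itself a ground for removal. It is not; the diary, like the pill count, is evidence of whether medication was taken.
- That removal loses all of a subject's eating-night data, so that only subjects who took and tolerated their capsules are analysed. Only the nights after removal are lost.
- That selective loss is established. It is a reasonable inference; no passage says who will be removed.
- That the bias is about one night per week. Taking 35% leavers with 2 nights/week on drug and 5 afterwards gives 0.35 x 3 = 1.05. That is an error in one arm's mean, and it cancels if both arms lose alike. It assumes a good last on-drug diary, although 4 of the 6 leavers in the case series stopped for lack of efficacy; applied only to the 2 side-effect leavers it is 2/17 x 3 = 0.35. It also assumes carry-forward and a Day 63 to 91 window, neither of which the plan specifies.

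**Conclusion.** The point holds in a limited form. The plan ties stopping study drug to leaving the study and plans no eating-night data between the early final visit and Day 91. The analysis labelled intent-to-treat is therefore exposed to informative loss.

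The size cannot be derived, since the documents give no removal rate, SD or endpoint window. Under the assumptions above, the effect on the comparison is about 0 with equal loss. At 35% against 10% outcome-related loss, the most unequal case tried, it is 0.17 to 0.37 nights/week with type I error 0.06 to 0.11. Those figures also assume that a removed subject has no value in the endpoint analysis. If diary nights up to removal were used instead, the error would be different and is equally unknown. This is an inexpensive improvement to data collection; it does not show that the trial's result would be wrong.

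**What to change.** In Study Medication Accountability and Compliance, Blinding and Early Withdrawal, separate stopping study medication from leaving the study. When and why medication stops remains a matter for the investigator's clinical judgement, unchanged by this proposal.

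- Do the final-visit procedures at discontinuation, as now planned.
- Then ask subjects who consent to keep the existing daily diary to Day 91. Dispense a diary at that visit and collect it by mail or at a brief return visit. The visit lists collect diaries only at clinic visits, so the telephone contacts can serve as reminders but not as a means of return.
- For subjects leaving treatment under these three sections, end diary collection only on withdrawal of consent or loss to follow-up.
- Flag nights recorded after study drug was stopped or after a code break, so that the analysis can identify them.

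The cost is amendment wording plus extra diaries and returns for perhaps 4 subjects (10% of 20 is 2 per arm) to 14 (35% of 20 is 7 per arm). Uptake will be partial, and some of the added nights will be off drug or unblinded.
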